**Table 3**

	Day of screening	Immediately pre procedure (within 1 hour)	7.5 mins (+/- 2.5mins)	2 hours (+/- 30 mins)	6 hours (+/- 30 mins)	24 hours (+/- 30 mins)
CXR	✓	✓				✓
Cardiorespiratory examination	✓					
NAP blood sampling (non-safety)			✓			
Bloods: FBC, U&E's, LFTs, CRP	✓			✓	✓	✓
ABG		✓		✓	✓	✓
Urine Collection for IMP (non-safety)			✓	✓		
Attending ICU consultant permission	✓					
Informed consent	✓			✓	✓	✓
Observations, pulse, temperature, oxygen saturation	✓	✓		✓	✓	✓
All ventilator settings, PEEP, oxygenation, P:F ratio	✓	✓		✓	✓	✓

## 5 STUDY POPULATION

Part A: The study population will be comprised exclusively of healthy male volunteers.

Part B: The study population will be comprised of male patients in ICU (RIE and WGH) with pulmonary infiltrates.

## 5.1 NUMBER OF PARTICIPANTS

A total of 6 participants will be recruited for Part A.

A total of 3 patients will be recruited for Part B.

## 5.2 INCLUSION CRITERIA FOR PART A

For part A, healthy male volunteers aged between 18 and 40.

## 5.3 INCLUSION CRITERIA FOR PART B

5.4 Ventilated male patients over the age of 18 in the ICU.

## 5.5 EXCLUSION CRITERIA FOR PART A

A patient will not be eligible for inclusion in the study if any of the following criteria apply at entry:

1. Age < 18 or >40 years
2. History of any chronic or ongoing acute illness (with particular reference to asthma, upper respiratory tract infection, lower respiratory tract infection, bronchiectasis, congenital heart disease, ischaemic heart disease, valvular heart disease, diabetes mellitus, chronic renal impairment, urinary tract infection)
3. Any current medication
4. Any history of previous reactions to fluorescein or any other anaphylaxis
5. Abnormal physical signs detected at cardiorespiratory examination
6. Temperature >37.3 degrees Celsius
7. Oxygen saturation <95% breathing room air
8. Haemoglobin, white cell count or platelet count outside the normal laboratory reference range
9. Blood sodium, potassium, urea, creatinine, bilirubin, alanine aminotransferase, random glucose or C-reactive protein outside the normal laboratory reference range
10. Forced expiratory volume in one second (FEV1) or forced vital capacity (FVC) <80% predicted
11. FEV1:FVC ratio <70%
12. Any significant cardiorespiratory abnormality detected on chest x-ray
13. Peripheral venous access insufficient to support 14 gauge cannulae.
14. General practitioner confirmation of eligibility as a healthy volunteer not received
15. Failure to provide suitable identification (passport/driving licence)
16. Refusal to consent to enter details in 'The Over Volunteering Prevention System' (TOPS) database
17. Positive urine drug screen
18. Participation in any other interventional study or less than three months since their last participation in an interventional study
19. Female

## 5.6 EXCLUSION CRITERIA FOR PART B

1. Age <18years
2. Any contraindication for bronchoscopy 
3. Refusal for participation by attending consultant
4. FiO2 >70%
5. PEEP>10cm
6. Recent pneumothorax (whilst on ventilator)
7. Any history of previous reactions to fluorescein or any other anaphylaxis
8. Participation in any other interventional study or less than three months since their last participation in an interventional study
9. Female

## **6 PARTICIPANT SELECTION AND ENROLMENT**

### **6.1 APPROACHING AND IDENTIFYING POTENTIAL PARTICIPANTS FOR PART A**

An advert will be placed on University of Edinburgh email lists and on University of Edinburgh notice boards. Potential participants will be asked to make contact with the research team only if they consider themselves to be healthy. Interested individuals will be invited to contact the research team who will send out information on the study (participant information sheets and consent forms). Participants sent such information will be invited to contact the research team to arrange a screening visit (section 6.3 below) or to decline participation. If no reply is received after 2 weeks, the research team will send a reminder.

### **6.2 APPROACHING AND IDENTIFYING POTENTIAL PARTICIPANTS FOR PART B**

After screening by members of the routine healthcare team in ICU, the patient or if incapacitated, their personal/professional legal representative will be approached by a member of the research team. A professional legal representative will be a clinician responsible for the medical treatment of the patient if they are independent of the study or a person nominated by the healthcare provider and will only be approached if a personal legal representative is not available. Direct face-to-face approach will be made. If the patient is conscious and the clinician in charge judges the patient to have capacity to provide informed consent then he will be approached directly. The first approach will always be by a member of the research team who is a qualified nurse or doctor.

### **6.3 SCREENING FOR ELIGIBILITY**

#### **For part A:**

Volunteers who contact the research team will be invited to attend for a screening visit. This will take the form of;

- a short history
- cardiorespiratory examination
- full blood count
- urea & electrolytes, liver function tests, random blood glucose, C-reactive protein
- CXR
- spirometry
- oxygen saturation
- urine toxicology screen
- consent for the study
- consent for details to be submitted to the TOPS database
- Volunteer's GP being contacted regarding health status and suitability to participate

These are performed with the sole intention of identifying potential exclusion criteria as listed in section 5.4.

A medically qualified member of the research team will perform the history, examination and investigations.

#### **For part B**

ICU patients will be screened by the ICU research team for inclusion and exclusion criteria.

### **6.4 CONSENTING PARTICIPANTS**

For healthy volunteers, eligible subjects will be asked to consider giving written consent. This will be taken by a medically qualified member of the research team.

In ICU, patients who are ventilated and are judged by the clinician in charge to be able to provide informed consent- they will be given a written information sheet fully explaining the procedure with expected benefits and potential outcomes and risks. Consent will be obtained by clinically qualified members of the team. For ventilated patients who are not able to consent,

their personal/professional legal representative will be approached by the research team in person-they will be given a written information sheet fully explaining the procedure with expected benefits and potential outcomes and risks.

Consent will be obtained by clinically qualified members of the team. One original will be signed and 2 copies made. The original will be filed in the patient's notes along with the Information sheet. One copy will be given to the patient/patients personal/professional legal representative and one stored in the trial master file (TMF).

## **6.5 INELIGIBLE AND NON-RECRUITED PARTICIPANTS**

For ineligible patients and eligible volunteers who are not subsequently entered into the study, the reason for ineligibility or non-recruitment will be entered on the paper CRF. Only anonymised data will be entered on to the paper CRF and this will include gender, age, "ineligible" or "non-recruitment" and the associated reason.

## **6.6 WITHDRAWAL OF STUDY PARTICIPANTS**

Participation in the study is voluntary. A participant has the right to discontinue or completely withdraw from the study at any time for any reason. The Investigator has the right to discontinue a participant from the study at any time if it is deemed to be in the volunteer's or patient's best interest. The reason and circumstances for premature discontinuation will be documented in the participant's Case Report Form (CRF).

### **6.6.1 Reasons for Discontinuing Participants**

Reasons for discontinuation of the study **may** include

#### Bronchoscopy

- intolerance of the scope (i.e. unable to intubate the trachea)
- marked coughing

### **6.6.2 Discontinuation Procedures**

If a participant chooses to withdraw completely from the study and all study assessments this will be recorded in the CRF. Any concerns expressed by the participant will be addressed by the research team.

## **7 INVESTIGATIONAL MEDICINAL PRODUCT AND PLACEBO**

### **7.1 STUDY DRUG**

#### **7.1.1 Study Drug Identification**

##### ***Neutrophil Activation Probe sterile solution (NAP)***

The final dosage form of the investigational medicinal product (IMP) consists of 80 µg (+/- 20%) of the drug substance NAP dissolved in 5 mL of sterile Phosphate Buffered Saline (PBS) pH 7.4 solution, presented in sterile nitrogen filled glass vials. The solution is intended for direct instillation into the distal lung delivery via a microcatheter at microdose levels (<100 µg). Upon contact with neutrophils and/or the enzyme elastase, NAP will give a specific fluorescent signal that will be detected by pCLE.

#### **7.1.2 Study Drug Manufacturer**

The synthesis of NAP is carried out using standard solid phase chemistry at a GLP compliant manufacturing site, Aptuit Laurus, India. No materials at risk of transmitting transmissible spongiform encephalopathy (TSE) are used in the manufacturing process. NAP manufacture and filling, under aseptic conditions, and QP release are performed by Pharmacy Production Unit, Western Infirmary, [name], and are carried out according to Good Manufacturing Practices. The quality of the product is controlled by ensuring

compliance to internal specifications set with due regard to European guidance on the control of IMPs.

### **7.1.3 Labelling and Packaging**

NAP labelling and packaging is being carried out by Pharmacy Production Unit, Western Infirmary, Glasgow.

### **7.1.4 Storage**

The IMP is to be stored at room temperature. Stability studies have been conducted to confirm the stability of NAP formulation over the proposed study duration. NAP will be stored in the pharmacy at the RIE.

## **7.2 OTHER MEDICATIONS**

### **7.2.1 Non-Investigational Medicinal Products**

Paracetamol (in the event of significant symptoms of fever)

Salbutamol (in the event of bronchospasm)

Oxygen (in the event of hypoxia)

Adrenaline (in the event of anaphylaxis).

## **8 STUDY ASSESSMENTS**

### **8.1 OUTCOME MEASURES**

#### **8.1.1 Primary Outcome Measures**

This is an exploratory clinical study. The primary outcome measure is measurement of fluorescence and imaging parameters determined using pCLE and Cellvizio viewer software.

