## 2 STUDY OBJECTIVES

### 2.1 OBJECTIVES

#### 2.1.1 Primary Objective

The primary objective is to deliver NAP as a microdose to 6 healthy volunteers and 3 patients in ICU and to test if **activated neutrophils within the alveolar space can be detected with NAP and pCLE over background autofluorescence**

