### 2.2 ENDPOINT MEASURES FOR EXPLORATORY CLINICAL STUDY

#### 2.2.1 Primary Endpoint

- Visualise the delivery of a microdose of NAP in healthy volunteers and ICU patients.
- Delineate the presence of activated neutrophils within CXR infiltrates in ventilated patients with suspected ALI/VAP.

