#### 4.1 A) Delivery of NAP to healthy volunteers

Volunteers will return on a morning agreed after the screening medical described in Section 7.1 below. A brief history (pertaining to upper and lower respiratory tract symptoms) and respiratory examination will be repeated. Spirometry will be performed before proceeding.

For Volunteers, 1-4, they will be bronchoscoped and pCLE performed of the right middle lobe (RML). Immediately following this, NAP will be instilled via microcatheter into the RML and pCLE performed again of the RML.

Bronchoscopy will be performed using a standardised protocol and procedure employed throughout our work thus far. Briefly, local anaesthesia will be applied topically to the throat. Sedation with intravenous midazolam will be optional. Electrocardiogram (ECG) trace and SpO2 will be monitored continuously. A flexible fibreoptic bronchoscope will be passed per-orum or nasally and the bronchoscope wedged into the medial segment of the right middle lobe. The alveoflex will be passed down the working channel and alveoscopy performed with upto 4 transbronchial passes. Following this, the alveoflex will be withdrawn and a microcatheter passed into the medial segment of the RML and NAP instilled. Immediately following this pCLE will be performed as described above.

For volunteers, 5 and 6, they will be bronchoscoped and pCLE performed of the right lower lobe (RLL) and right middle lobe (RML). Immediately following this, NAP will be instilled via microcatheter into the RLL and RML and pCLE performed again of the RLL and RML. The dose of NAP will be divided between 2 segments in the RLL and one segment in the RML. The volunteer will receive a total of 80mcg (+/-20%) NAP.

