#### **4.2 B) Delivery of NAP to 3 patients in ICU with pulmonary infiltrates**

ICU patients will be screened daily by ICU research nurses. If they fit the inclusion criteria described in Section 5.3, they or their personal/professional legal representative will be approached by a member of the research team to obtain consent. The attending consultant will also be approached and only after also gaining permission from the attending consultant will the patient be considered for inclusion into the study.

The pulmonary infiltrates will be identified on a CXR, which has been performed as part of routine clinical care and bronchoscopy and pCLE performed as above. A CXR will be performed immediately before the procedure. pCLE will be performed on areas without infiltrates as well as the affected segment/s. Following this, NAP will be instilled into the affected segment/s and unaffected segment/s via a microcatheter . A total of 80 mcg ( $\pm$ 20%) of NAP will be delivered

to the patient divided between the affected and unaffected segments. pCLE will be subsequently performed on the segments in which NAP has been delivered. We have performed bronchoscopy in over 70 patients in ICU over the last 5 years. The whole procedure including delivery of NAP will take approximately 30 minutes. The table below summarise the events and data to be collected before and after the procedure.

In addition, we intend to collect an additional sample (less than 5 ml) at  $t = 7.5$  mins ( $\pm 2.5$  mins) for analysis to demonstrate the systemic uptake, or lack thereof, of the IMP. For these participants, the urometer will be emptied at the time of bronchoscopy and then any urine passed over the next 2 hours will be collected to demonstrate the systemic uptake, or lack thereof, of the IMP.

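### The protocol does not provide for masked reading of the pCLE images behind the primary outcome, which leaves the Part B affected-versus-unaffected contrast open to reader bias

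*Protocol*

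**What the plan says.** Section 8.1.1 of the protocol gives the whole definition of the outcome: "The primary outcome measure is measurement of fluorescence and imaging parameters determined using pCLE and Cellvizio viewer software". The primary objective (2.1.1) asks whether activated neutrophils "can be detected with NAP and pCLE over background autofluorescence". The second primary endpoint (2.2.1) is to "Delineate the presence of activated neutrophils within CXR infiltrates in ventilated patients with suspected ALI/VAP".

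The imaging provides two within-participant contrasts:

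- **Before versus after NAP, both parts.** For volunteers 1-4 (4.1) the right middle lobe is imaged, then "NAP will be instilled via microcatheter into the RML and pCLE performed again of the RML". Volunteers 5 and 6 follow the same sequence, with the dose split over three segments. In Part B (4.2), after instillation, "pCLE will be subsequently performed on the segments in which NAP has been delivered".
- **Affected versus unaffected segment, Part B only.** Infiltrates are located on a routine chest X-ray, a further film is taken just before the procedure, and "pCLE will be performed on areas without infiltrates as well as the affected segment/s".

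On numbers, section 5.1 states "A total of 6 participants will be recruited for Part A" and "A total of 3 patients will be recruited for Part B".

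The protocol names no image reader, no masking and no reading order. The DMSC provisions (4.1 and 11.2) concern safety and permission to proceed, not image reading.

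**The concern.** Whoever quantifies the images knows the answer the study hopes for: more signal in an infiltrate than outside it, and more after NAP than before. As written, that person may have performed the bronchoscopy, with the X-ray already seen, and may belong to the team that developed the probe (Lay Summary). If the reading leaves any discretion over which image run or area to measure, that knowledge can push the result in the expected direction.

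Little in the design would expose this. Tables 2 and 3 list no independent measure of neutrophils or elastase in the imaged segments. The internal comparators (pre-NAP images and unaffected segments) would be read with the same knowledge.

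At stake is the proof of concept in three ICU patients. The Lay Summary ties follow-on funding for a validation study to safety and the ability to image activated neutrophils. The Professional Summary expects demonstration in ICU to lead directly to validation trials.

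**Working it through.** The protocol gives no power, effect size or variance for this outcome, so there is no figure of its own to reproduce beyond the participant count: 6 + 3 = 9.

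**Step 1. Which images carry which contrast.** Count one set per segment and time point, taking at least one affected and one unaffected segment per ICU patient:

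| Participants | Segments | Time points | Sets |
|---|---|---|---|
| Volunteers 1-4 | 1 | 2 | 4 × 1 × 2 = 8 |
| Volunteers 5-6 | 3 | 2 | 2 × 3 × 2 = 12 |
| ICU patients | at least 2 | 2 | 3 × 2 × 2 = 12 (minimum) |
| Total | | | at least 32 |

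Segment status varies only in the 12 Part B sets. In the other 8 + 12 = 20 there is only timing to mask. These are sets, not files; if passes are stored separately there are more files.

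**Step 2. Illustration of selective reading.** Section 4.1 allows up to 4 transbronchial passes in Part A (per segment for volunteers 5 and 6), and section 4.2 refers back to that procedure. Assume k = 4 candidate passes per segment, independent and roughly normal, with no true difference between segments. The reader takes the brightest pass in the affected segment and one typical pass in the unaffected segment.

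- Mean false difference = expected maximum of 4 standard normals = 1.03 SD (simulation, 200,000 draws), where SD is the pass-to-pass SD.
- Chance of the expected direction in one patient = k/(k + 1) = 4/5 = 0.80.
- Chance in all three patients = 0.80³ = 0.51.
- The same without selection = 0.5³ = 0.125.

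**Step 3. Sensitivity.** With k = 2 the mean is 0.56 SD, and the chance in all three patients is (2/3)³ = 0.30. If the passes within a segment share a correlation r, the mean difference falls to 1.03 × √(1 − r): 1.03 × 0.707 = 0.73 SD at r = 0.5, and 1.03 × 0.447 = 0.46 SD at r = 0.8, in units of the total SD. Both values of r are assumptions.

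The number of candidate images actually read, their correlation and the reader's behaviour are not in the protocol. These figures show a direction and an order of size, not an estimate for this trial.

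**The case against.** The case against has several parts, and some of it stands.

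- **Silence is not a statement.** The protocol does not say that reading is unmasked. That is correct, and the point is only that masking is not provided for.
- **Frame and region rules may sit elsewhere.** They are commonly left to an SAP or imaging manual, which is not at hand. A reader might infer that their absence is itself an error; the document does not support that. A fixed rule alone would also remove the selection illustrated above. Masking is different: recordings must be coded before anyone reads them, so it is a matter of conduct that a protocol fixes.
- **Scope.** A reader might infer that the primary outcome is compromised to the same degree in all nine participants. It is not. Segment status exists only in the three ICU patients, and a bright post-NAP image may reveal its timing whatever code it carries.
- **Built-in comparisons.** Pre-NAP images, unaffected segments and healthy lungs are real controls. They do not protect against a reader who knows which is which.
- **Exploratory status.** There is no test and no success threshold, so no stated error rate is inflated. The first primary endpoint is simply to visualise delivery. The remaining consequence is a possibly biased proof-of-concept reading that feeds the follow-on decision.
- **Acquisition.** Probe placement and choice of passes at the bedside cannot be masked, and masked reading leaves that untouched.

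**Conclusion.** The point holds in a limited form. The protocol makes no provision for masked reading of the images behind its primary outcome. This matters most for the affected-versus-unaffected contrast in the three Part B patients, where segment status is known before imaging. Pre/post timing is a lesser concern in all nine participants.

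The size of any bias cannot be obtained from the document. The figure of about 1.0 SD rests on four independent passes, one-sided selection and no true effect, and it shrinks with correlation. A reader might infer that a positive result would be an artefact, or that a quantified bias has been shown; neither follows. The conclusion also assumes that the images are stored and quantified after the procedure, which the mention of viewer software suggests but the protocol does not state.

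This is a cheap improvement, not a flaw that invalidates the study.

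**What to change.** Add to section 8.1.1 that:

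1. pCLE recordings will be exported under random codes that hide participant, segment status and time point.
2. They will be quantified in random order under one frame and region rule set before reading starts. The rule itself may be kept in the SAP or imaging manual.
3. The reader will preferably be an existing team member who did not perform that bronchoscopy.
4. Codes will be broken only after the values are locked.

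The main gain is masking affected against unaffected segments in the three ICU patients. The cost is data handling for at least 32 segment-by-time-point sets, and more files if passes are stored separately. No procedure, visit, sample size or additional staff is affected. Two limits should be acknowledged in the text: post-NAP timing may remain guessable, and image acquisition stays unmasked.

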#### **8.1.2 Other Measured Variables**

Safety in part A and part B and initial proof of concept in ICU to detect neutrophil activation.

#### **8.1.3 Processing and Analysis of Blood Samples**

'Screening visit' and all other blood samples will be sent to the hospital laboratories for assessment of full blood count, urea and electrolytes, blood glucose, liver function tests and C-reactive protein.

### **8.2 SAFETY ASSESSMENTS**

#### **8.2.1 Clinical**

In part A, Clinical assessment will be on a rolling basis throughout the study days (table 2). 'Vital signs' (pulse, blood pressure, temperature and oxygen saturation) will be measured on arrival and at least hourly ( $\pm 10$ mins) over the course of the day. The only exceptions will be that monitoring will be suspended overnight if the volunteer is sleeping comfortably. In this exception, the volunteer can be observed directly and continuous heart rate monitoring will continue, and additional monitoring can be re-initiated immediately if there are any features of clinical distress. During bronchoscopy there is continuous monitoring of ECG trace and oxygen saturation. Spirometry in part A will be a primary safety assessment with a greater than 15% reduction from baseline defined as significant.

In part B, patients will be within ICU and be continually monitored.

